6.8.1. Rescue Medicine

There is no rescue therapy to reverse the AEs observed with PF-06650833 or OC; standard medical supportive care must be provided to manage the AEs.

7. DISCONTINUATION OF STUDY INTERVENTION AND PARTICIPANT DISCONTINUATION/WITHDRAWAL

7.1. Discontinuation of Study Intervention

It may be necessary for a participant to permanently discontinue study intervention. Reasons for permanent discontinuation of study intervention include the following: liver injury, ECG changes, acute kidney injury, pregnancy, or laboratory abnormalities. Please refer to subsections [7.1.1](#) through [7.1.5](#) for details of each.

If study interventions are permanently discontinued, the participant will not remain in the study for further evaluation. See the [SoA](#) for data to be collected at the time of discontinuation of study interventions.

In the event of discontinuation of study intervention, it must be documented on the appropriate CRF/in the medical records whether the participant is discontinuing further receipt of study interventions or also from study procedures, posttreatment study follow-up, and/or future collection of additional information.

7.1.1. Liver Injury

All of the following laboratory abnormalities require discontinuation if they are confirmed:

AST or ALT that meet ANY of the following:

- $>3 \times \text{ULN}$ with at least one total bilirubin value $>2 \times \text{ULN}$.
- $>3 \times \text{ULN}$ accompanied by signs or symptoms consistent with hepatic injury (eg, new onset elevated PT/INR).
- Two sequential AST or ALT elevations $>5 \times \text{ULN}$, regardless of total bilirubin or accompanying signs or symptoms.

7.1.2. ECG Changes

A participant who meets either bulleted criteria based on the average of triplicate ECG readings will be withdrawn from the study interventions.

- QTcF >500 msec.

- Change from baseline: QTcF >60 msec and QTcF >450 msec.

If a clinically significant finding is identified (including, but not limited to, changes from baseline in QTcF after enrollment), the investigator or qualified designee will determine if the participant can continue in the study and if any change in participant management is needed. This review of the ECG printed at the time of collection must be documented. Any new clinically relevant finding should be reported as an AE.

7.1.3. Potential Cases of Acute Kidney Injury

Abnormal values in SCr concurrent with presence or absence of increase in BUN that meet the criteria below, in the absence of other causes of kidney injury, are considered potential cases of acute kidney injury and should be considered important medical events.

An increase of ≥ 0.3 mg/dL (or ≥ 26.5 μ mol/L) in SCr level relative to the participant's own baseline measurement should trigger another assessment of SCr as soon as practically feasible, preferably within 48 hours from awareness.

If the second assessment (after the first observations of ≥ 0.3 mg/dL [or ≥ 26.5 μ mol/L] in SCr relative to the participant's own baseline measurement) is ≥ 0.4 mg/dL (or ≥ 35.4 μ mol/L), the participant should be discontinued from the study and adequate, immediate, supportive measures taken to correct apparent acute kidney injury.

Participants should return to the investigator site and be evaluated as soon as possible, preferably within 48 hours from awareness of the second assessment confirming abnormal SCr result. This evaluation should include laboratory tests, detailed history, and physical assessment. In addition to repeating SCr, laboratory tests should include serum BUN, serum creatine kinase, and serum electrolytes (including at a minimum potassium, sodium, phosphate/phosphorus, and calcium), in addition to urinary dipstick, urine microscopic examination, and urinary indices. All cases confirmed on repeat testing as meeting the laboratory criteria for acute kidney injury, with no other cause(s) of laboratory abnormalities identified, should be considered potential cases of drug-induced kidney injury irrespective of availability of all the results of the investigations performed to determine etiology of the abnormal SCr. If ≥ 2 healthy participants in a given period are noted to have 2 consecutive SCr results of ≥ 0.3 mg/dL (or ≥ 26.5 μ mol/L), an assessment of whether the finding may be considered an adverse drug reaction should be undertaken.

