7.1.5. Laboratory Abnormalities

All of the following laboratory abnormalities require discontinuation if they are confirmed:

- ANC $< 750/\text{mm}^3$ ($< 0.75 \times 10^9/\text{L}$).

- Hemoglobin <9.0 g/dL (<5.59 mmol/L or <90 g/L) or a decrease of >30% from baseline (either criterion or both).
- Platelet count <75,000/mm³ (<75.0 × 10⁹/L).
- ALC <500/mm³ (<0.5 × 10⁹/L).

NOTE: Participants with ALC <500/mm³ (0.5 × 10⁹/L) will be reflex tested for FACS-TBNK until the absolute lymphocyte count resolves or stabilizes at a level acceptable to the investigator and sponsor.

- CK >10 × ULN.

NOTE: Urine myoglobin and SCr will be performed as reflex testing for any participant with CK >10 × ULN

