In the majority of DILI cases, elevations in AST and/or ALT precede TBili elevations ($>2 \times$ ULN) by several days or weeks. The increase in TBili typically occurs while AST/ALT is/are still elevated above $3 \times$ ULN (eg, AST/ALT and TBili values will be elevated within the same laboratory sample). In rare instances, by the time TBili elevations are detected, AST/ALT values might have decreased. This occurrence is still regarded as a potential DILI. Therefore, abnormal elevations in either AST OR ALT in addition to TBili that meet the criteria outlined below are considered potential DILI (assessed per Hy’s law criteria) cases and should always be considered important medical events, even before all other possible causes of liver injury have been excluded.

The threshold of laboratory abnormalities for a potential DILI case depends on the participant’s individual baseline values and underlying conditions. Participants who present with the following laboratory abnormalities should be evaluated further as potential DILI (Hy’s law) cases to definitively determine the etiology of the abnormal laboratory values:

- Participants with AST/ALT and TBili baseline values within the normal range who subsequently present with AST OR ALT values $>3 \times$ ULN AND a TBili value $>2 \times$ ULN with no evidence of hemolysis and an alkaline phosphatase value $<2 \times$ ULN or not available.
- For participants with baseline AST **OR** ALT **OR** TBili values above the ULN, the following threshold values are used in the definition mentioned above, as needed, depending on which values are above the ULN at baseline:
 - Preexisting AST or ALT baseline values above the normal range: AST or ALT values >2 times the baseline values AND $>3 \times$ ULN; or $>8 \times$ ULN (whichever is smaller).
 - Preexisting values of TBili above the normal range: TBili level increased from baseline value by an amount of at least $1 \times$ ULN **or** if the value reaches $>3 \times$ ULN (whichever is smaller).

Rises in AST/ALT and TBili separated by more than a few weeks should be assessed individually based on clinical judgment; any case where uncertainty remains as to whether it represents a potential Hy's law case should be reviewed with the sponsor.

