10.7. Appendix 7: ECG Findings of Potential Clinical Concern

ECG Findings That May Qualify as AEs

Marked sinus bradycardia (rate <40 bpm) lasting minutes.New PR interval prolongation >280 msec.New prolongation of QTcF to >480 msec (absolute) or by \geq60 msec from baseline.New-onset atrial flutter or fibrillation, with controlled ventricular response rate: ie, rate <120 bpm.New-onset type I second-degree (Wenckebach) AV block of >30 seconds' duration.Frequent PVCs, triplets, or short intervals (<30 seconds) of consecutive ventricular complexes.
ECG Findings That May Qualify as SAEs

QTcF prolongation >500 msec.New ST-T changes suggestive of myocardial ischemia.New-onset left bundle branch block (QRS >120 msec).New-onset right bundle branch block (QRS >120 msec).Symptomatic bradycardia.Asystole:
In awake, symptom-free participants in sinus rhythm, with documented periods of asystole \geq3.0 seconds or any escape rate <40 bpm, or with an escape rhythm that is below the AV node.In awake, symptom-free participants with atrial fibrillation and bradycardia with 1 or more pauses of at least 5 seconds or longer.Atrial flutter or fibrillation, with rapid ventricular response rate: rapid = rate >120 bpm.Sustained supraventricular tachycardia (rate >120 bpm) ("sustained" = short duration with relevant symptoms or lasting >1 minute).

- Ventricular rhythms >30 seconds' duration, including idioventricular rhythm (heart rate <40 bpm), accelerated idioventricular rhythm (HR >40 bpm to <100 bpm), and monomorphic/polymorphic ventricular tachycardia (HR >100 bpm (such as torsades de pointes)).
- Type II second-degree (Mobitz II) AV block.
- Complete (third-degree) heart block.

ECG Findings That Qualify as SAEs

- Change in pattern suggestive of new myocardial infarction.
- Sustained ventricular tachyarrhythmias (>30 seconds' duration).
- Second- or third-degree AV block requiring pacemaker placement.
- Asystolic pauses requiring pacemaker placement.
- Atrial flutter or fibrillation with rapid ventricular response requiring cardioversion.
- Ventricular fibrillation/flutter.
- At the discretion of the investigator, any arrhythmia classified as an adverse experience.

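### In Protocol Section 7.1.3 the cluster rule for creatinine names neither an increase nor baseline, so unchanged creatinine meets it as written; the 0.4 mg/dL discontinuation limit has a milder form of the same fault.

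*Protocol*

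**What the plan says.** Protocol Section 7.1.3 states a serum creatinine limit four times.

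1. **Repeat-test trigger.** An increase of at least 0.3 mg/dL (26.5 µmol/L) over the participant's "own baseline measurement should trigger another assessment of SCr as soon as practically feasible".
2. **Parenthesis on the first observation.** The same 0.3 mg/dL, still tied to the participant's baseline, but without the word *increase*.
3. **Discontinuation limit.** After that parenthesis closes, the sentence continues "own baseline measurement) is" at least 0.4 mg/dL (35.4 µmol/L). If so, "the participant should be discontinued from the study and adequate, immediate, supportive measures taken to correct apparent acute kidney injury".
4. **Cluster rule.** If at least two "healthy participants in a given period are noted to have 2 consecutive SCr results of" at least 0.3 mg/dL (26.5 µmol/L), then "an assessment of whether the finding may be considered an adverse drug reaction should be undertaken".

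Neither document restates the cluster rule or the 0.4 mg/dL limit anywhere as a change from baseline. Protocol Section 7.1 lists acute kidney injury among the reasons for permanent discontinuation and adds that a participant so discontinued does not stay in the study for further evaluation.

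**The concern.** The cluster sentence is the main fault. A *result* is a measured concentration, and nothing in the sentence turns it into a change. Read on its own, it is met by two participants whose creatinine never moved, provided it is 0.3 mg/dL or more. A rule meant to pick out a possible drug effect across participants would then not separate a rise from ordinary values.

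The discontinuation limit has a weaker version of the fault. Baseline is mentioned just before the 0.4 mg/dL figure, but inside a parenthesis that grammatically describes only the first observation. The operative statement is that the second assessment itself is at least 0.4 mg/dL. A reader may infer that a rise is meant, but the sentence does not say so.

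Both are operative safety limits. One decides when a possible adverse drug reaction has to be assessed; the other decides whether a participant leaves a study that plans to dose about 10 and needs at least 8 to complete.

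**Working it through.** **Inputs from the Protocol.** Limits of 0.3 mg/dL (26.5 µmol/L) and 0.4 mg/dL (35.4 µmol/L), and the two-participant threshold (Section 7.1.3). About 10 enrolled, at least 8 completing (Section 9.5). Creatinine is part of the safety panel (Appendix 2). As the Schedule of Activities reads, safety laboratory tests fall on Period 2 Days 9, 11 and 12, so two consecutive results within that period are routine.

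**Assumption.** The documents give no creatinine levels. Baseline *b* is taken as 0.4 to 1.0 mg/dL.

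**Step 1: are the numbers themselves intact?** 26.5/0.3 = 88.3 and 35.4/0.4 = 88.5, equal within rounding. Equivalently, 35.4/26.5 = 1.336 against 0.4/0.3 = 1.333. The unit pairs agree, so the figures are sound and only words are missing.

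**Step 2: what each statement specifies.**

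| Statement | Says *increase* | Has its own reference to baseline |
|---|---|---|
| Repeat-test trigger, 0.3 | yes | yes |
| Parenthesis, 0.3 | no | yes |
| Discontinuation limit, 0.4 | no | no (only in the parenthesis) |
| Cluster rule, 0.3 | no | no |

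**Step 3: written against intended limits (mg/dL).** The intended cluster limit is *b* + 0.3 and the written one is 0.3. The intended discontinuation limit is *b* + 0.4 and the written one is 0.4.

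| Assumed *b* | Intended cluster limit | Unchanged result *b* meets written / intended | Intended discontinuation limit | Repeat equal to *b* meets written / intended |
|---|---|---|---|---|
| 0.4 | 0.7 | yes / no | 0.8 | yes / no |
| 0.6 | 0.9 | yes / no | 1.0 | yes / no |
| 0.8 | 1.1 | yes / no | 1.2 | yes / no |
| 1.0 | 1.3 | yes / no | 1.4 | yes / no |

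The last column applies only after a first value of at least *b* + 0.3 (0.7 to 1.3 mg/dL). If *b* were below 0.4, a full return to baseline would not meet the written discontinuation limit.

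**Step 4: how easily the cluster threshold is reached.** Two participants are 2/10 = 20% of those enrolled or 2/8 = 25% of the minimum completing. If every participant's unchanged value is at least 0.3 mg/dL, all 10 of 10 count with no rise. Even if each participant independently had only a 50% chance of being at or above 0.3 mg/dL (an assumption chosen to be cautious), the probability that at least two qualify is

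- 8 participants: 1 − (1 + 8)/2^8 = 1 − 9/256 = 0.965
- 10 participants: 1 − (1 + 10)/2^10 = 1 − 11/1024 = 0.989

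**Step 5: direction of the error.** If the rise is at least 0.3 and *b* is positive, the value *b* + rise is also at least 0.3; the same holds for 0.4. The literal limits therefore catch every case that the intended limits catch. They can only add false alarms.

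**Step 6: wording elsewhere in the Protocol.** Appendix 7 separates the two kinds of limit explicitly: "New prolongation of QTcF to >480 msec (absolute) or by" 60 msec or more from baseline. Appendix 6 on liver safety has "TBili level increased from baseline value by an amount of at least" 1 × ULN. Section 7.1.5 has, next to an absolute haemoglobin limit, "a decrease of >30% from baseline (either criterion or both". In these criteria a change is named as a change.

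**The case against.** The strongest reply is that the cluster sentence should not be read alone. The section opens by speaking of abnormal creatinine values, defines the criterion as an increase over baseline, and uses the same pair of figures (0.3 and 26.5) in the cluster rule. That rule directly follows a sentence on cases confirmed by repeat testing, so its two consecutive results are most naturally the first and repeat assessments just described. On this view the wording is shorthand for a criterion already defined.

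The reply is stronger still for the 0.4 mg/dL limit. Its sentence names baseline and speaks of correcting apparent kidney injury, and the next sentence describes the second assessment as confirming an abnormal result. A value back at baseline confirms nothing of the kind. Section 8 also has safety issues discussed with the sponsor to decide whether a participant continues. Nor is the Protocol uniformly strict about wording: Section 8.2.3 once gives a QTcF limit from baseline without the word *increase*, although it does keep *baseline*.

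Most of this stands. The intent can be recovered from context, the 0.4 mg/dL limb is the lesser one, and Step 5 shows that no renal signal would be missed. The figure of 10 out of 10 describes the literal rule and does not predict what site staff would do. These points keep the matter minor. They do not make the cluster sentence correct, because a safety limit should carry its own reference point and this one has none.

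**Conclusion.** The concern holds. As written, the cluster rule is an absolute limit of 0.3 mg/dL where a rise of 0.3 mg/dL over baseline is plainly meant. The gap between the two equals the baseline itself, 0.4 to 1.0 mg/dL over the assumed range, and unchanged creatinine meets the written limit throughout that range. The discontinuation limit has the same gap, but it bites only after a genuine first rise of at least 0.3 mg/dL and for a baseline of at least 0.4 mg/dL.

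The sizes rest on the assumed baseline range; the wording fault does not. The consequence is limited to possible over-alerting and, in a narrow case, an unnecessary discontinuation. The cluster rule prompts an assessment and stops nobody, and neither the primary pharmacokinetic analysis nor the sample size is affected. This is a low-priority correction that is worth making because it is free.

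**What to change.** Change two sentences in Protocol Section 7.1.3.

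- **Cluster rule:** require two consecutive SCr results *each showing an increase of ≥0.3 mg/dL (≥26.5 µmol/L) over the participant's own baseline*.
- **Discontinuation limit:** apply it if the second assessment *shows an increase of ≥0.4 mg/dL (≥35.4 µmol/L) over the participant's own baseline*.

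With these words an unchanged value meets neither limit at any baseline, and a participant whose repeat has returned to baseline is not discontinued. The thresholds, visit schedule and analyses stay as they are. The cost is a few words, with no operational burden.

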7.1.4. Pregnancy

In the case of a positive serum pregnancy test, the participant will have investigational product stopped and result re-confirmed via a second urine test or serum sample collected on the same day (or as soon as possible) and submitted to the laboratory for pregnancy testing.

7.1.5. Laboratory Abnormalities

All of the following laboratory abnormalities require discontinuation if they are confirmed:

- ANC $< 750/\text{mm}^3$ ($< 0.75 \times 10^9/\text{L}$).

- Hemoglobin <9.0 g/dL (<5.59 mmol/L or <90 g/L) or a decrease of >30% from baseline (either criterion or both).
- Platelet count <75,000/mm³ (<75.0 × 10⁹/L).
- ALC <500/mm³ (<0.5 × 10⁹/L).

NOTE: Participants with ALC <500/mm³ (0.5 × 10⁹/L) will be reflex tested for FACS-TBNK until the absolute lymphocyte count resolves or stabilizes at a level acceptable to the investigator and sponsor.

- CK >10 × ULN.

NOTE: Urine myoglobin and SCr will be performed as reflex testing for any participant with CK >10 × ULN

7.2. Participant Discontinuation/Withdrawal From the Study

A participant may withdraw from the study at any time at his/her own request. Reasons for discontinuation from the study include the following:

- Refused further study procedures;
- Lost to follow-up;
- Death;
- Study terminated by sponsor;
- At the discretion of the investigator for safety, behavioral, compliance, or administrative reasons.

At the time of discontinuing from the study, if possible, an early discontinuation visit should be conducted. See the [SoA](#) for assessments to be collected at the time of study discontinuation and follow-up and for any further evaluations that need to be completed.

The early discontinuation visit applies only to participants who are enrolled and then are prematurely withdrawn from the study. Participants should be questioned regarding their reason for withdrawal.

The participant will be permanently discontinued from the study interventions and the study at that time.

If a participant withdraws from the study, he/she may request destruction of any remaining samples taken and not tested, and the investigator must document any such requests in the site study records and notify the sponsor accordingly.

If the participant withdraws from the study and also withdraws consent (see [Section 7.2.1](#)) for disclosure of future information, no further evaluations should be performed and no additional data should be collected. The sponsor may retain and continue to use any data collected before such withdrawal of consent.

7.2.1. Withdrawal of Consent

Participants who request to discontinue receipt of study intervention will remain in the study and must continue to be followed for protocol-specified follow-up procedures. The only exception to this is when a participant specifically withdraws consent for any further contact with him or her or persons previously authorized by the participant to provide this information. Participants should notify the investigator in writing of the decision to withdraw consent from future follow-up, whenever possible. The withdrawal of consent should be explained in detail in the medical records by the investigator, as to whether the withdrawal is only from further receipt of study intervention or also from study procedures and/or posttreatment study follow-up, and entered on the appropriate CRF page. In the event that vital status (whether the participant is alive or dead) is being measured, publicly available information should be used to determine vital status only as appropriately directed in accordance with local law.

7.3. Lost to Follow up

A participant will be considered lost to follow-up if he or she repeatedly fails to return for scheduled visits and is unable to be contacted by the study site.

The following actions must be taken if a participant fails to attend a required study visit:

- The site must attempt to contact the participant and reschedule the missed visit as soon as possible. Counsel the participant on the importance of maintaining the assigned visit schedule and ascertain whether the participant wishes to and/or should continue in the study.
- Before a participant is deemed lost to follow-up, the investigator or designee must make every effort to regain contact with the participant (where possible, 3 telephone calls and, if necessary, a certified letter to the participant's last known mailing address or local equivalent methods). These contact attempts should be documented in the participant's medical record.
- Should the participant continue to be unreachable, he/she will be considered to have withdrawn from the study.

8. STUDY ASSESSMENTS AND PROCEDURES

The investigator (or an appropriate delegate at the investigator site) must obtain a signed and dated ICD before performing any study-specific procedures.

Study procedures and their timing are summarized in the [SoA](#). Protocol waivers or exemptions are not allowed.

Safety issues should be discussed with the sponsor immediately upon occurrence or awareness to determine whether the participant should continue or discontinue study intervention.

Adherence to the study design requirements, including those specified in the [SoA](#), is essential and required for study conduct.

All screening evaluations must be completed and reviewed to confirm that potential participants meet all eligibility criteria. The investigator will maintain a screening log to record details of all participants screened and to confirm eligibility or record reasons for screening failure, as applicable.

Participants will be screened within 28 days prior to administration of the study intervention to confirm that they meet the study population criteria for the study. If the time between screening and dosing exceeds 28 days as a result of unexpected delays (eg, delayed drug shipment), then participants do not require rescreening if the laboratory results obtained prior to first dose administration meet eligibility criteria.

A participant who qualified for this protocol but did not enroll from an earlier cohort/group may be used in a subsequent cohort/group without rescreening, provided laboratory results obtained prior to the first dose administration meet eligibility criteria for this study. In addition, other clinical assessments or specimen collections, eg, banked biospecimens, may be used without repeat collection, as appropriate.

Every effort should be made to ensure that protocol-required tests and procedures are completed as described. However, it is anticipated that from time to time there may be circumstances outside the control of the investigator that may make it unfeasible to perform the test. In these cases, the investigator must take all steps necessary to ensure the safety and well-being of the participant. When a protocol-required test cannot be performed, the investigator will document the reason for the missed test and any corrective and preventive actions that he or she has taken to ensure that required processes are adhered to as soon as possible. The study team must be informed of these incidents in a timely manner.

If an IV catheter is utilized for blood sample collections, ECGs and vital sign assessments (pulse rate and BP) should be collected prior to the insertion of the catheter.

For samples being collected and shipped, detailed collection, processing, storage, and shipment instructions and contact information will be provided to the investigator site prior to initiation of the study.

The total blood sampling volume for individual participants in this study is approximately 350 mL. The actual collection times of blood sampling may change. Additional blood samples may be taken for safety assessments at times specified by Pfizer, provided the total volume taken during the study does not exceed 550 mL during any period of 56 consecutive days.

To prepare for study participation, participants will be instructed on the information in the [Lifestyle Considerations](#) and [Concomitant Therapy](#) sections of the protocol.

